### **10.2. Treatment Phase**

The subject will arrive to the clinic in the morning, having fasted for at least 8 hours prior to dosing, at which time the following procedures will be completed:

#### **10.2.1. Treatment Visit 1 (Day 0)**

The following procedures will be carried out at this visit.

1. The subject will be asked about any severe hypoglycemic events (requiring the assistance of another person) since the screening visit.

- a. If a severe hypoglycemic event has occurred in the 2 weeks prior to the admission, the visit will be postponed until it has been at least 2 weeks since the last severe hypoglycemic event.
2. If it has been more than 30 days since the Screening Visit, venous blood will be collected for a repeat of baseline hematology and serum chemistry assessments. However, the treatment visit may continue based upon qualification at the Screening Visit.
3. The subject will be questioned and any changes in concomitant medications will be documented in the CRF.
4. For females of child-bearing potential, a urine pregnancy test will be performed
  - a. If positive, the subject will be discontinued from the study.
  - b. Full vital signs, including triplicate BP, will be assessed after a 5-minute seated rest. Heart rate and single BP will be repeated immediately prior to dosing and at 30, 60, 120 and 180 minutes post, with  $\pm$  10 minutes per collection time point.
5. Insertion of intravenous catheter for blood sampling.
  - a. Starting plasma glucose level will be assessed:
    - i. If  $>300$  mg/dL, ketones will be checked
    - ii. If ketones are found to be moderate or greater, the visit will be postponed.
6. Optional placement of a CGM for assessment of glucose levels during the induction phase.
  - a. If used, the CGM will be calibrated against glucose measurements obtained from the point-of-care, rapid glucose analyzer.
7. Insulin infusion will be started as described in Section 7.2.
  - a. Those subjects using injection therapy will have a second intravenous catheter inserted in the other arm for insulin infusion.
  - b. Plasma glucose levels will be measured no more than 10 minutes apart while the plasma glucose level is  $\geq 100$  mg/dL and no more than 5 minutes apart when the plasma glucose level is  $< 100$  mg/dL.
8. Once an initial plasma glucose measurement  $< 80$  mg/dL is achieved,
  - a. The basal rate will be returned to normal for subjects using an insulin pump and the insulin infusion will be stopped for subjects using insulin injections.
  - b. A first baseline PK blood sample should be collected at the point that plasma glucose first reaches a concentration  $< 80$  mg/dL.
9. After 5 minutes, a confirmatory plasma glucose measurement will be performed.
  - a. If plasma glucose remains  $< 80$  mg/dL, collect a second baseline PK blood sample, and begin administration of the study drug (see Section 9.3.2).
  - b. If plasma glucose has risen to  $\geq 80$  mg/dL, return to step 7b and repeat the process.
10. Following study dosing, plasma glucose will be measured every  $5 \pm 2$  minutes until 90 minutes post-dosing.

11. Additional blood samples will be collected at 10, 20, 30, 45, 60, 90, 120, and 180 minutes post-dosing, with  $\pm 5$  minutes per collection, and processed and stored at  $-80 \pm 20$  C for determination of plasma glucagon levels.
12. After completing all collections and procedures at 180 minutes post-dosing, the subject will be given a meal as per the standard practice at each site, and their usual dose of insulin. The subject can then leave the clinic after plasma glucose is confirmed to be between 70 and 180 mg/dL.
13. Local tolerability will be assessed as follows:
  - a. Subjects will complete age-appropriate questionnaires regarding injection site discomfort ([Appendix 1](#)) at  $10 \pm 5$  and  $30 \pm 5$  minutes post-dosing, and again at  $180 \pm 5$  minutes post-dosing if the FPS score reported at 30 minutes is  $> 0$ .
  - b. An investigator will use the modified Draize scales ([Appendix 2](#)) to assess erythema and edema formation at the injection site at  $10 \pm 5$  and  $30 \pm 5$  minutes following administration. Any injection site with a score  $> 0$  for either erythema or edema at 30 minutes post-dosing will be re-evaluated for both at  $180 \pm 5$  minutes post-dosing.
14. Adverse events reported by the subject or observed by an investigator will be recorded in Advantage eClinical and managed as medically appropriate.

If a subject exhibits signs of distress at any time post-dosing or if plasma glucose drops below  $< 70$  mg/dL, glucose tablets may be given at the discretion of the investigator. Signs and symptoms should be monitored and if the subject's condition fails to improve within 15 minutes, additional glucose tablets or other intervention (e.g., IV dextrose) may be given at the discretion of the investigator. Every attempt should be made to complete all remaining safety and efficacy evaluations, to the extent this can be done while safeguarding the subject.

#### **10.2.2. Treatment Visit 2 (7-28 days after the first treatment)**

Subjects ages 12- $<18$  will return for a second visit at least 7 days and no more than 28 days following the first treatment visit. The procedures to be followed at this visit are as listed in [Section 10.2.1](#), but the 0.5 mg dose of G-Pen™ (glucagon injection) will be given. If scheduled more than 28 days after the first treatment, body weight will be assessed at the second treatment visit.

#### **10.2.3. Follow-Up Phone Call (3-14 days after the final treatment)**

The parent or guardian will be contacted by telephone within 3-14 days of completing each dosing visit or premature discontinuation. This phone call will include the following assessments:

1. Review of changes in concomitant medications.
2. Adverse event questioning by asking the subjects to respond to a non-leading question such as "how do you feel?"

If the subject cannot be reached by 14-days post-treatment, a registered letter will be sent to the parent/guardian to facilitate scheduling of the follow-up phone call.

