**Table 4: Schedule of Assessments**

Assessment	Screening	Treatment 1	Treatment 2*	Follow-up
	CRC Visit Day -30 to -3	CRC Visit Day 0	CRC Visit 7-28 days after first treatment	Phone call 3-14 days after each treatment
Informed consent	x	—	—	—
Inclusion/exclusion review	x	—	—	—
Height and weight	x	—	(x)	—
Physical exam a	x	—	—	—
Demographic data	x	—	—	—
Medical History	x	—	—	—
Concomitant medications	x	x b	x b	x b
Urine pregnancy test, if applicable	x	x	x	—
Hematology/Clinical chemistry	x	—	—	—
HbA1c	x	—	—	—
Vital signs	x	x	x	—
Overnight fast from midnight	—	x	x	—
Administration of study medication	—	x	x	—
Subject questionnaires for injection site discomfort	—	x	x	—
Draize scales for erythema/edema	—	x	x	—
Glucagon levels (PK) c	—	x	x	—
Venous blood glucose (PD) d	—	x	x	—
Adverse events (AE)	x	x	x	x b

\*Subjects ages 12-<18 only.

(x) Applies to weight only; repeat if >28 days have passed since the Treatment 1 visit.

a Excluding breast and pelvic/genital exams.

b Changes from prior visit.

c Venous blood at -5, 0, 10, 20, 30, 45, 60, 90, 120, and 180 minutes post dose, with ±2 minutes per collection for the samples from -5 and 0 minutes, and ±5 minutes for later samples.

d Via rapid glucose analyzer at -5, 0, and every 5 minutes post dose to 90 minutes, with ±2 minutes per collection.

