### 12.3. Reporting Period

For all AEs, the reporting period begins from the time the subject provides informed consent, through the Follow-up Visit. All adverse events will be followed until resolution or the subject is medically stable or the subject exits the study.

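### The follow-up call's adverse event question is put to the child and asks about the present, whereas Table 4 and Section 12.3 need events since the last visit

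*Protocol*

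**What the plan says.** - **Who is called, and when.** Protocol Section 10.2.3: "The parent or guardian will be contacted by telephone within 3-14 days of completing each dosing visit or premature discontinuation".
- **What is asked.** The call has two items. Item 1 is "Review of changes in concomitant medications". Item 2 is "Adverse event questioning by asking the subjects to respond to a non-leading question such as" followed by the example "how do you feel".
- **What the schedule expects.** The follow-up column of Table 4 is headed "Phone call 3-14 days after each treatment". Its AE entry carries footnote b, "Changes from prior visit".
- **What is reportable.** Section 12.3: "the reporting period begins from the time the subject provides informed consent, through the Follow-up Visit".
- **Who counts as a source.** Section 12.8 names what the investigator observes and what the subject reports spontaneously, and adds that each subject is questioned. It gives no wording, recall period or parent respondent. Section 10.2.1 item 14 likewise names only the subject and the investigator.
- **A different account of the call.** Section 7.1 describes one call, after the final dose, at 3 ± 14 days.

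**The concern.** AE incidence is a listed endpoint (Protocol 5.3.2, SAP 1.2.2), and safety in each age group is a secondary objective (Protocol 5.2). Children aged 2-<12 have one treatment visit and may leave after the 180-minute procedures, a meal and a glucose check. What happens at home then reaches the database mainly through this call.

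Two features of item 2 limit what it can collect. The example concerns how the child is at that moment, so it does not prompt for something that started and settled earlier. It is also addressed to the child, although the adult on the telephone is the one who watched the child at home. For a young child, delayed vomiting that has stopped is the kind of event that could go unrecorded.

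**Working it through.** No figure in the plan depends on this point, so the check compares the texts and counts the scheduled contacts.

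**1. Period covered.** Footnote b of Table 4 sets the interval as the time since the prior visit, and Section 12.3 makes events in that interval reportable. The example in Section 10.2.3 asks about the time of the call. Its item 2 states no recall period and asks for no onset or stop dates.

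**2. Respondent.** Section 10.2.3 telephones the parent or guardian but puts the AE question to the subjects. Sections 10.2.1 (item 14) and 12.8 do not repair this. By contrast, Section 9.4 requires both subjects and their adult guardians to be asked about concomitant medications, so the protocol names the guardian where medications are concerned but not for AEs. The SAP's mock-up table of discomfort onset and duration allows for some children aged 2-<6 being too young to understand that questionnaire.

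**3. Scheduled AE enquiries after leaving the clinic** (Protocol 7.1, 10.2.2, 10.2.3, Table 4):

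| Situation | Enquiries | First one after the dose |
|---|---|---|
| Ages 2-<12, single dose | 1 (call) | day 3-14 |
| Ages 12-<18, after dose 1, by Table 4 and the body of 10.2.3 | 2 (call, Visit 2) | day 3-14 |
| Ages 12-<18, after dose 1, by Section 7.1 | 1 (Visit 2) | day 7-28 |
| Ages 12-<18, after the final dose | 1 (call) | day 3-14 by Table 4 and 10.2.3 |

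For ages 12-<18 the total is 2 + 1 = 3 under Table 4, or 1 + 1 = 2 under Section 7.1.

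**4. Calendar.** The earliest call is on day 3. An event that starts on the dosing day (day 0) and lasts under 2 days has ended by then. A question about the present would not prompt for it.

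**5. Timing of the call.** Section 7.1 has one call after the final dose. The body of 10.2.3, Table 4, SAP 1.1 and the SAP's mock-up Table 4 have one after each treatment, while the heading of 10.2.3 refers to the final treatment. Taken literally, 3 ± 14 days runs from 3 − 14 = −11 to 3 + 14 = 17 days, which does not match 3-14 days and begins before the dose.

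**The case against.** The best defence is that the plan already contains the interval. Footnote b states it, and the wording in 10.2.3 is an example, so the actual requirement is a non-leading question. Item 1 of the call reviews medication changes, which would reveal treated events. Section 12.2 makes observed or volunteered AEs reportable without limiting who volunteers them. Section 10.2.3 also uses the word subject loosely: if the subject cannot be reached, a letter goes to the parent. A sensible coordinator would speak to the parent about the days since the visit.

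Most of this stands, and it limits the point to events that may be missed. It does not remove the point. The footnote gives the intent, but 10.2.3 is the instruction for making the call, and its only printed question does something narrower. Staff at about eight clinics could use that question as their script.

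A reader might infer more than the documents support:

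- **That this call is the only AE contact for everyone.** After dose 1 in ages 12-<18, Visit 2 carries a scheduled AE assessment. Through the Section 10.2.1 procedures it also asks about severe hypoglycemic events since screening.
- **That interval events are not elicited at all.** Footnote b, the medication review and volunteered reports are all routes by which they can be recorded.
- **That the loss can be put as a percentage.** If a 24-hour event began at a uniformly random time between dose and call, it would be present at the call with probability of about 24/72 = 33% on day 3, 24/168 = 14% on day 7 and 24/336 = 7% on day 14. The arithmetic is right. But it assumes the example is used verbatim, footnote b is ignored, the medication review reveals nothing and no one volunteers anything. The duration and the onset pattern are also assumed. It does not estimate loss in this trial.
- **That cleared injection-site reactions are being lost.** Under Section 12.2 these are AEs only if they need medical intervention, and local tolerability is assessed separately in the clinic.
- **That AE comparisons across ages are biased.** The SAP tabulates AEs by dose, not by age. The synopsis mentions comparing AE reports between groups, but no such test is planned.

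**Conclusion.** The point holds as a minor one. Section 10.2.3 item 2 does not carry out the interval review that Table 4 footnote b and Section 12.3 require, and no text names the parent or guardian as an AE respondent. Where the call is the only scheduled enquiry after discharge (ages 2-<12, and the final dose in ages 12-<18), short events that resolved before it may be missed. This is most plausible in children too young to report for themselves.

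The conclusion assumes that at least some callers would use the printed example as it stands and that some families would not volunteer a resolved event. The documents give no means of sizing either. The primary analysis, the sample size and the planned tests are unaffected. What is affected is the completeness of a descriptive safety endpoint.

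**What to change.** 1. In Protocol 10.2.3 item 2, replace the example with an open, non-leading question to the parent or guardian, and to the child where able, covering the time since the last visit. For instance: *Has your child had any health problems since leaving the clinic on [date]?* Record onset and stop dates.
2. In Protocol 12.8, name the parent or guardian as a source of AE reports.
3. Reconcile Protocol 7.1, 10.2.3 (heading and body) and Table 4 on whether the call follows each dose or only the final one, and on 3 ± 14 versus 3-14 days. Check that SAP 1.1 and its mock-up Table 4 agree with the result.

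The cost is a sentence in each of two sections, the timing correction, and the wording that sites use on the call. The downside is slightly more AEs recorded and some recall error, greatest when the call is made near day 14.

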### **10.3. Subject Withdrawal**

Subjects may withdraw from the study at any time at their own request, or they may be withdrawn at any time at the discretion of the investigator or Sponsor for safety, behavioral or administrative reasons. If a subject does not return for a scheduled visit, every effort should be made to contact the subject to determine the reason(s) why the subject failed to return for the scheduled visit, and to reschedule the missed visit. In any circumstance, every effort should be made to document subject outcome. Information regarding the reason for not completing the study will be recorded in the CRF. The investigator should inquire about the reason for withdrawal, request that the subject return for a final visit, and follow-up with the subject regarding any unresolved AEs. It will be documented whether or not each subject completed the study. Any subject who receives at least one treatment dose of study medication will be included in the safety analysis.

If a decision by the investigator or sponsor is made to withdraw a subject exposed to at least one dose of study drug, a follow-up phone call should be completed as per Section 10.2.3.

If a subject is to be withdrawn from the study during a treatment visit, every attempt should be made to complete all remaining safety and efficacy evaluations, to the extent this can be done while safeguarding the subject.

If the subject withdraws from the study and also withdraws consent, no further evaluations should be performed, and no additional data should be collected. The Sponsor may retain and continue to use any data collected before such withdrawal of consent.

**Table 4: Schedule of Assessments**

Assessment	Screening	Treatment 1	Treatment 2*	Follow-up
	CRC Visit Day -30 to -3	CRC Visit Day 0	CRC Visit 7-28 days after first treatment	Phone call 3-14 days after each treatment
Informed consent	x	—	—	—
Inclusion/exclusion review	x	—	—	—
Height and weight	x	—	(x)	—
Physical exam a	x	—	—	—
Demographic data	x	—	—	—
Medical History	x	—	—	—
Concomitant medications	x	x b	x b	x b
Urine pregnancy test, if applicable	x	x	x	—
Hematology/Clinical chemistry	x	—	—	—
HbA1c	x	—	—	—
Vital signs	x	x	x	—
Overnight fast from midnight	—	x	x	—
Administration of study medication	—	x	x	—
Subject questionnaires for injection site discomfort	—	x	x	—
Draize scales for erythema/edema	—	x	x	—
Glucagon levels (PK) c	—	x	x	—
Venous blood glucose (PD) d	—	x	x	—
Adverse events (AE)	x	x	x	x b

\*Subjects ages 12-<18 only.

(x) Applies to weight only; repeat if >28 days have passed since the Treatment 1 visit.

a Excluding breast and pelvic/genital exams.

b Changes from prior visit.

c Venous blood at -5, 0, 10, 20, 30, 45, 60, 90, 120, and 180 minutes post dose, with ±2 minutes per collection for the samples from -5 and 0 minutes, and ±5 minutes for later samples.

d Via rapid glucose analyzer at -5, 0, and every 5 minutes post dose to 90 minutes, with ±2 minutes per collection.

## 11. ASSESSMENTS

Every effort should be made to ensure that the protocol required tests and procedures are completed as described. However, it is anticipated that there may be circumstances outside the control of the investigator, who will take all steps necessary to ensure the safety and well-being of the subject. When a protocol-required test cannot be performed, the investigator will document the reason(s) and any corrective and preventive actions taken to ensure that study processes are adhered to as soon as possible. The study team and the sponsor will be informed of these incidents in a timely fashion.

For all blood and urine samples collected, all efforts must be made to obtain these samples at the same clock time as well as time periods specified in the Schedule of Activities. In addition, visits to the site must occur within the pre-defined windows outlined in this protocol otherwise they will be considered as protocol deviations

### 11.1. Blood Volume

There will be approximately 30 PD samples of about 2cc each and 10 PK samples of 2 cc each drawn for a total of about 80 cc per treatment visit. This may be reduced by use of a CGM during the induction phase. Subjects ages 2-<12 will complete a single treatment visit, while subjects 12-<18 will complete two such visits 7 to 28 days apart. There will be a 13.5 cc sample at Screening for a clinical chemistry panel, hematology and HbA1c determination. A total of about 94 cc of blood will be drawn over the total study for subjects 2-<12 years of age and about 174 cc for subjects ages 12-<18 (Table 5).

**Table 5: Frequency and Volume of Blood Collections**

Sample Type	Sample Volume (mL)	Blood Volume (mL) by Sample Type/Visit			Total Volume (mL)
		Screening	Treatment Visit #1	Treatment Visit #2	
Clinical Chemistry	7.5	7.5	-	-	7.5
Hematology	3	3	-	-	3
HbA1c	3	3	-	-	3
Pharmacodynamics a	2	-	40-60*	40-60*	60/120
Pharmacokinetics	2	-	20	20	20/40
Total	2-7.5	13.5	60-80	60-80	93.5/173.5

a Single plasma glucose measurements at bedside via rapid glucose analyzer.

### Volume of Blood Draws

The maximum blood volume to be collected will not exceed 5% of the subject's blood volume. The number of blood draws will be reduced for subjects who do not weigh enough to allow for the full schedule to be completed. Early collections (-5 to 30 minutes) will be preferred over later blood draws, and PD samples will be prioritized over PK samples.

## 11.2. Clinical Laboratory Tests

The tests outlined in Table 6 will be performed at the specified time points described in the Schedule of Activities.

**Table 6: Clinical and Safety related Laboratory Tests Performed at Site**

Hematology	Chemistry	Urine	Laboratory
WBC count	Glucose	$\beta$ -hCG a	HbA1c
RBC count	Creatinine		Glucagon levels
Hemoglobin	Na +		
Hematocrit	K +		
Platelet count	Ca ++		
	Albumin		
	Alkaline Phosphatase		
	AST/SGOT		
	ALT/SGPT		

a Female subjects of childbearing potential require a negative urine pregnancy test at Screening and prior to dosing for each of the 2 Treatment Visits. Pregnancy testing will be repeated as the Follow-up visit for safety reasons.

Each site's local laboratory will be utilized for analysis of all variables with the exception of urine pregnancy tests, glucagon and rapid plasma glucose measurements made during treatment visits. Local laboratory procedures will be followed. Each laboratory will provide their Clinical Laboratory Improvement Act (CLIA) certification and normal ranges to the Sponsor or its designee.

Each site will locally source point-of-care urine pregnancy tests.

A central analytical lab will analyze the PK samples collected in this study. The procedures for preparing, storing and shipping PK samples to the analytical lab will be outlined in a manual that will be provided by the lab to all investigators prior to initiation of the study.

During post-treatment evaluations, plasma glucose levels will be measured using a bedside rapid glucose analyzer (Analox, YSI or equivalent). The glucose analyzer will be calibrated before each subject visit and sites will maintain a log of calibration results. To reduce the total volume of blood needed for smaller subjects, a continuous blood glucose monitor may be substituted during the induction phase only (see Section 7.2).

## 11.3. Vital Signs

The BP and heart rate will be measured at the times specified in the Schedule of Activities. Additional collection times, or changes to collection times of BP and heart rate using automated device is permitted, as necessary, to ensure appropriate subject's safety.

BP and heart rate will be measured in the supine position with the subject's arm supported at the level of the heart, and recorded to the nearest mmHg. The dominant arm will be used throughout the study. The subject should be rested for at least 5 min before the BP is obtained.

Measurements of both the BP and heart rate must be taken at least 2 min apart and recorded in the CRF.

## 12. SAFETY AND ADVERSE EVENT (AE) REPORTING

### 12.1. Definition of an Adverse Event

An AE is any untoward medical occurrence in a clinical investigation subject administered a pharmaceutical product and which is not necessarily required to have a causal relationship with this treatment. An AE can therefore be any unfavorable and unintended sign, symptom, or disease temporally associated with the use of a medicinal product, whether or not considered related to the medicinal product. Examples of AEs include:

- Abnormal test findings
- Clinically significant symptoms and signs
- Changes in physical examination findings which are untoward and deemed clinically significant by the investigator.
- Allergy/hypersensitivity

The criteria for determining whether an abnormal objective test finding may be reported as an AE are as follows:

- Test result is associated with accompanying symptoms,
- Test result requires additional diagnostic testing or medical/surgical intervention,
- Test result leads to a change in study dosing or discontinuation from the study, significant additional concomitant drug treatment or other treatment, or
- Test result is considered to be an AE by the investigator or Sponsor.

Repeat of a test based on an abnormal result in the absence of the above conditions does not constitute an AE. Any abnormal test result determined to be an error does not require reporting as an AE.

A treatment-emergent AE (TEAE) is an AE that either commenced following initiation of study treatment or was present prior to study treatment but increased in frequency or severity following initiation of study treatment.

Standard medical terminology should be used in describing AEs. Informal descriptions should be avoided.

